2 STUDY OBJECTIVES

2.1 Primary Objective

The primary objective is to assess the safety and tolerability of Octaplas in the pediatric population by monitoring SAEs, ADRs, TEs, TEEs and hyperfibrinolytic events, including laboratory parameters for metabolic derangements, renal function, and hematologic implications.

2.2 Secondary Objective(s)

The secondary objective is to assess the efficacy of Octaplas in the pediatric population by measuring hemostatic parameter improvements reflecting changes in hemostasis.

3 INVESTIGATIONAL PLAN

3.1 Primary and Secondary Endpoints

Primary Endpoint(s)

- Incidence of SAEs, ADRs (e.g., allergic reactions; refer to **Section 7.3.2.1** for definition), TEs, TEEs and hyperfibrinolytic events, beginning after the start of the first infusion episode until the final examination (end of safety follow-up period).
- Clinically significant changes in laboratory parameters to assess for metabolic derangements, renal function, and hematologic implications as measured by the following: Chem 7 (metabolic panel), complete blood count (CBC) and ionized calcium (refer to **Section 7.3.5.3** for definition).

Due to the complex and highly variable and individual medical circumstances and interventions that are to be expected in this study, no single parameter or measurement of outcome is chosen as the primary endpoint.

Secondary Endpoint(s)

- Clinically significant changes in hemostatic parameters as measured by the following: international normalized ratio (INR), prothrombin time (PT), activated partial thromboplastin time (aPTT), thromboelastography (TEG), or thromboelastometry (ROTEM).
- Volume (dose in mL/kg) of Octaplas used per infusion episode for each patient.
- Medically significant changes in vital signs.
- Investigator's assessment of overall safety observed for each patient.

3.2 Overall Study Timeline

The study started in the second quarter 2015 and is planned for completion by 4th quarter of 2017. The end of the study is defined as the last visit of the last patient participating in the study.

Study Flow Chart

Time-Points	Screening/ Pre-Infusion (within 7 days prior to start of first infusion¹)	72-Hour Study Treatment Period (Infusion Episode(s)^{2,3}	72-Hour Safety Follow-up Period ^{3,4}	Final Examination 72 hours after end of last study infusion episode²
Inclusion/Exclusion criteria	X			
Informed consent/assent	X			
Physical examination ⁵	X			
Medical history (incl. prior and current relevant concomitant medications ⁶)	X			
Vital signs ⁷	X	X		X
Documentation of the type of surgical procedure indicated ⁸	X			
Demographic data	X			
Blood group determination	X			
Hemostatic parameters ⁹	X	X		
Laboratory parameters (Chem 7, CBC and ionized calcium) ⁹	X	X		X
Pregnancy test ¹⁰	X			
Ordering of plasma	X			
Administration of Octaplas		X		
Investigator Assessment of Safety ¹¹				X
Monitoring of SAEs and ADRs		←-----Continuously-----→		
Monitoring of TEs, TEEs, and hyperfibrinolytic events (regardless of causality) ¹²				
Monitoring concomitant medication				

1. Screening time window of -7 days does not apply for informed consent/assent procedure.
2. An infusion episode is defined as any amount of Octaplas given, with no more than 60 minutes break between 2 Octaplas infusions. If the time interval between the end of one Octaplas infusion and the beginning of the next Octaplas infusion is more than 60 minutes this will be counted as 2 different infusion episodes. For patients on CPB who are primed with plasma, a transfusion episode will begin with the initiation of the circuit with plasma and will end when the heparin is reversed during the process of coming off CPB. The study Treatment Period will end after 72 hours from the start of the first infusion of Octaplas, or after the end of the last infusion episode if the total duration of Octaplas treatment is <72 hours.
3. Single donor plasma (e.g. FFP, FP24, thawed plasma, etc.) should be avoided during the Treatment and Follow-up study periods. Patients receiving single donor plasma during the Treatment or Follow-up periods will be withdrawn from the trial. Plasma exchange, TPE or plasmapheresis is not permitted during the Treatment or Follow-up periods. Patients who develop the need for and undergo plasma exchange or plasmapheresis will be withdrawn from the trial.
4. The permitted visit window for the Safety Follow-up period and Final Examination is 72 hours (\pm 6 hours) after the end of the last Octaplas infusion. The Follow-up procedures (e.g., Investigator assessment of safety) may be performed sooner if it will not be practical to obtain at the 72-hour post final examination visit. If it is not medically feasible to obtain the final examination visit assessments at the 72 hours (\pm 6 hours) time point, the reason must be documented (e.g., patient discharged prior to 72 hours after the end of the last infusion, etc.).
5. A physical examination will be performed at the screening visit in accordance with the site's local standard procedures. This may include examination of dermatological and lymphatic system, head, eyes, ears, nose, throat [HEENT], respiratory tract, cardiovascular and gastrointestinal system, musculoskeletal system, neurological system, and endocrinological systems.
6. Details of any relevant prior (up to 7 days before the first administration of Octaplas) and concomitant medications administered during the trial period will be recorded on the case report form (CRF). All other transfusion products (e.g., albumin, cryoprecipitate, platelets) must be captured individually in the CRF. Routine medications that are considered standard and/or that have little or no impact on the study data results are not to be entered into the CRF (e.g., anesthesia medications, beta blockers, etc.). For details please see **Section 4.2**.
7. Vital signs will include heart rate, respiratory rate, temperature, arterial saturation and blood pressure assessment. Vitals should be assessed within a maximum of 6 hours before the start and 60 minutes after the end of the first infusion episode. All subsequent assessments should be accomplished within 60 minutes before and 60 minutes after each infusion episode. If multiple vital sign assessments are taken within 60 minutes before and/or after the infusion, the vital signs that are assessed closest before the start and after the end of each infusion should be recorded.
8. The type of surgical procedure indicated as well as start and stop dates and times of the procedure, estimated blood loss, use of ECMO and/or CPB will be recorded on the CRF.
9. Pre- and post-infusion episode samples for hemostatic and laboratory parameters will be tested. Pre-infusion samples for the first infusion episode should be drawn within 6 hours prior to the start of the first infusion episode (all the subsequent pre-infusion assessments are to be done within 60 minutes prior the infusion episode). Post-infusion episode samples should be drawn within 30 to 60 minutes after the end of each infusion. If the patient requires priming of the cardiopulmonary bypass (CPB) circuit with plasma, the post-infusion episode samples should be drawn 30-60 minutes after reversal of heparin during the process of coming off CPB. For the first infusion episode it is mandatory that, pre- and post-infusion episode samples for hemostatic and laboratory parameters be tested. If subsequent infusion episodes are performed, pre- and post-infusion episode laboratory tests should be performed unless considered not medically necessary by the Investigator (e.g., the timing of the pre-infusion episode sample is close to or overlaps with the timing of the post-infusion episode sample and it is not necessary to perform, etc.). In the event the pre- or post-infusion laboratory sample(s) are not drawn, the reason for not obtaining the sample(s) will be recorded on the CRF. If multiple hemostatic and laboratory parameters may be assessed before and/or after the infusion, the hemostatic and laboratory parameters that are assessed closest before the start and after the end of each infusion should be entered in the eCRF. TEG with Kaolin activation or ROTEM EXTEM testing should be performed as defined in **Section 7.3.5.3**.

10. Females \geq 11 years old or females of childbearing potential (if younger than 11 years old) must have a negative pregnancy test prior to the first infusion episode to qualify for the study.
11. This Assessment of Safety should be performed by the principal investigator or sub-investigator.
12. For this trial a “clinically relevant hyperfibrinolytic event” is defined by one of the following test results in the presence of a bleed that requires intervention:
 - Kaolin TEG – estimated percentage lysis (EPL) $>$ 7.5% at 30 min (after starting assay).
 - ROTEM EXTEM – maximum lysis (ML) $>$ 7.5% at 30 min (after starting assay).

Laboratory Evaluations Flow Chart¹

Time-Points	Pre-Infusion	Post-Infusion	Final Examination
	Before infusion episode	Between 30 and 60 minutes after each infusion episode	72 hours after end of last study infusion episode
Hemostatic parameters: INR, PT, aPTT, TEG or ROTEM	X	X	
Laboratory parameters: 
 • Chem 7 panel: BUN, CO₂ (bicarbonate), serum chloride, serum creatinine, glucose, serum potassium, and serum sodium. • CBC: WBC, RBC, platelets, hemoglobin, hematocrit, MCV, MCH, MCHC, and RDW. • Ionized calcium 	X	X	X

1. The following blood volume limits for sampling are recommended, if an Investigator decides to deviate from these, this should be justified. NIH Clinical Center Guidelines for Blood Drawn for Research Purposes in the Clinical Center (M95-9) rev 06/05/2009: For pediatric patients, no more than 5 mL/kg may be drawn for research purposes in a single day, and no more than 9.5 mL/kg may be drawn over any eight-week period.

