- Pre- and post-infusion episode samples for hemostatic and laboratory parameters will be tested. The pre-infusion episode laboratory samples should be drawn within 6 hours before the start of the first infusion episode and within 60 minutes prior to the start of subsequent infusion episodes. Post-infusion episode samples should be drawn within 30 to 60 minutes after the end of each infusion episode. If the patient requires priming of the cardiopulmonary bypass (CPB) circuit with plasma, the post-infusion episode samples should be drawn 30-60 minutes after reversal of heparin during the process of coming off CPB. For the first infusion episode it is mandatory that pre- and -post-infusion episode laboratory testing is performed. If subsequent infusion episodes are performed, pre- and post-infusion episode laboratory tests should be performed unless considered not medically necessary by the Investigator (e.g., the timing of the pre-infusion episode sample is close to or overlaps with the timing of the post-infusion episode sample and it is not necessary to perform, etc.). In the event pre- or post-infusion laboratory sample(s) are not performed, the reason will be documented in the CRF. If multiple hemostatic and laboratory parameters may be assessed before and/or after the infusion, the hemostatic and laboratory parameters that are assessed closest before the start and after the end of each infusion should be entered in the eCRF.

Safety Follow-up Period

- ADRs, TEs, TEEs, hyperfibrinolytic events and concomitant medications will be monitored for 72 hours (± 6 hours) after the last Octaplas transfusion is completed.

Final Examination

Seventy-two hours (\pm 6 hours) after the end of the last study infusion episode, a Final Examination will be performed that consists of the following assessments:

- Vital signs (see **Section 7.3.6**).
- Physician Assessment of Safety (**Section 7.3.1**).
- Blood sample(s) for laboratory parameters (see **Section 7.3.5.3**).
- Monitoring of ADRs (refer to **Section 7.3.2** for definition), TEs, TEEs, hyperfibrinolytic events and concomitant medications.

After the Final Examination, the clinical phase of the study is considered completed for the patient. No further study-related assessments will be performed, unless safety concerns (e.g., on-going ADRs) require follow-up.

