3.2. Study Endpoints (Target Variables)

3.2.1. Primary Endpoints

The primary (safety) endpoints are:

- Incidence of SAEs, ADRs (e.g., allergic reactions), TEs, TEEs and hyperfibrinolytic events, beginning after the start of the first infusion episode until the final examination (end of safety follow-up period).
- Clinically significant changes in laboratory parameters to assess for metabolic derangements, renal function, and hematologic implications as measured by the following: Chem 7 (metabolic panel), complete blood count (CBC), calcium and ionized calcium.

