Examples of protocol deviations to be considered in this respect would be violations of the study entry criteria, dosing errors, the use of forbidden concomitant medications, or the occurrence of completely unrelated medical events that require an interruption of the study procedures. The final decision regarding inclusion/exclusion of patients from the analysis sets will be taken by a panel including the Clinical Project Manager, the study statistician and a medical expert during a data review meeting before database lock. The decisions taken will be based on a review of complete data listings, and documented before the database is locked and the analysis is performed.

8. General Issues for Statistical Analysis

Descriptive summaries will be presented for each of the primary and secondary variables. In general, summaries will be completed for all patients overall and by groups of particular interest as indicated by the data. Continuous, quantitative variable summaries will include the number of patients with non-missing values (N), mean, standard deviation, median, minimum and maximum, 1st and 3rd quartile.

Categorical, qualitative variable summaries will include the frequency and percentage of patients who are in the particular category. In general the denominator for the percentage calculation will be the total number of patients in the analysis population unless otherwise specified.

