8.3. Handling of Missing Data

In general, missing data will not be imputed.

No analyses of the patterns of missing data will be done.

For medications the following will be applied: A medication will be assumed to be concomitant if it can be definitely shown that the medication was administered after start of the first Octaplas infusion and before the end of the observation period. Missing dates will not be replaced.

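### The primary-endpoint window ends at a final examination that may take place before 72 hours, so incidence may be understated and the planned tables would not show it

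*Protocol*

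**What the plan says.** **The endpoint window.** Protocol Section 3.1 counts events "beginning after the start of the first infusion episode until the final examination (end of safety follow-up period". SAP Section 3.2.1 ends the window in the same way: "until the final examination (end of safety follow-up period". Neither states an hour.

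**The examination date.** Protocol Section 3.2, flow-chart note 4, places the examination at 72 ± 6 hours after the last infusion. It then says that follow-up procedures, with the investigator's safety assessment as the example, "may be performed sooner if it will not be practical to obtain at the 72-hour post final examination visit". No earliest time is given. The next sentence asks for a documented reason when assessments cannot be made at 72 hours, for instance "patient discharged prior to 72 hours after the end of the last infusion".

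**After the examination.** Protocol Section 6.1: "After the Final Examination, the clinical phase of the study is considered completed for the patient". Later assessments happen only if there is a safety concern.

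**The monitoring period.** The same Section 6.1 says "ADRs, TEs, TEEs, hyperfibrinolytic events and concomitant medications will be monitored for 72 hours", with a ±6 hour tolerance, after the last transfusion. The protocol synopsis and SAP Section 4.1 state 72 (±6) hours as well. None of them makes an exception for an early examination.

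**The analysis.** The safety population is every treated patient (SAP Section 7). As a general default, "the denominator for the percentage calculation will be the total number of patients in the analysis population" (SAP Section 8). SAP Section 11.1 reports incidence as the number and percentage of patients; the only rate it adds is events per infusion. SAP Section 8.3 does not impute and states: "No analyses of the patterns of missing data will be done".

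**The concern.** Read literally, the endpoint closes for each patient on the day of that patient's final examination, and that day may be brought forward. A child examined 24 hours after the last infusion would then contribute 24 hours of follow-up but count as one whole patient without an event. Compared with incidence over the full window, lost observation can only lower the count or leave it unchanged.

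Nothing in the SAP would reveal this. It defines no follow-up duration, no rule for patients whose observation ends early and no rate per unit of time. Event listings give the time since the last dose for patients with events, but not the time at risk for those without.

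Incidence of SAEs, ADRs, TEs, TEEs and hyperfibrinolytic events is a primary endpoint of a post-marketing safety requirement. In a descriptive study the estimates are the result. SAP Section 5.2 also plans incidences with 95% confidence intervals by age, diagnosis and type of surgery. If early discharge differs between those groups, the comparison mixes risk with length of observation. The planned look in SAP Section 11.1 for events that become more frequent over time likewise needs the number of patients still under observation.

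**Working it through.** The plan states no expected incidence, no expected share of early examinations and no power calculation (SAP Section 6), so there is no figure to reproduce. The check asks only for the direction and plausible size.

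**Inputs from the documents.** N = 50. Treatment lasts up to 72 h (Protocol Section 6.2). Follow-up is 72 ± 6 h, that is 66 to 78 h. Planned observation per patient therefore runs from about 0 + 66 = 66 h to 72 + 78 = 150 h.

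**Assumptions.** True full-window incidence I = 10%. A fraction f of patients (10, 30 or 50%) is examined s hours after the last infusion and the rest at 72 h. Treatment lasts T0, either near 0 or 72 h. Observation stops at the examination, and its timing is unrelated to risk. The hazard is either constant or front-loaded with a 12 h half-life after the infusion.

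**Formula.** Observed incidence = (1 − f) × I + f × [1 − exp(−H(T0 + s))], where H is the cumulative hazard and H over the full window equals −ln(1 − I) = 0.1054.

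**One case in full.** T0 near 0, constant hazard, s = 24 h, f = 30%. H(24) = 0.1054 × 24/72 = 0.0351, so 1 − exp(−0.0351) = 0.0345. Observed incidence = 0.7 × 0.10 + 0.3 × 0.0345 = 0.0804. Relative bias = 0.0804/0.10 − 1 = −19.6%. Expected patients with an event: 50 × 0.0804 = 4.02 instead of 5.00.

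| Treatment time, hazard, examination | f = 10% | f = 30% | f = 50% |
|---|---|---|---|
| near 0 h, constant, 24 h | −6.5% | −19.6% | −32.7% |
| near 0 h, constant, 48 h | −3.2% | −9.7% | −16.1% |
| near 0 h, constant, 66 h (inside the tolerance) | −0.8% | −2.4% | −4.0% |
| 72 h, constant, 24 h | −3.2% | −9.7% | −16.1% |
| 72 h, constant, 48 h | −1.6% | −4.8% | −8.0% |
| near 0 h, front-loaded, 24 h | −2.3% | −6.9% | −11.4% |
| near 0 h, front-loaded, 48 h | −0.5% | −1.4% | −2.3% |

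Every entry is downward. Examinations before 24 h would lose more.

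**Against sampling error.** The exact 95% interval for 5/50 is 3.3% to 21.8%. The worst row moves the estimate from 10% to 6.73%, a shift of 3.27 percentage points. The lower arm of the interval is 10 − 3.3 = 6.7 points. The bias is the smaller of the two, but the reported interval does not contain it. Similarly, 0/50 gives an upper limit of 7.1% that reads as if all 50 patients had been fully observed.

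**What a sensitivity incidence would do.** Restrict the denominator to fully observed patients plus any patient who had an event before observation ended. In the case above this gives 0.0804 / (0.7 + 0.3 × 0.0345) = 0.0804/0.7104 = 11.3%. It leans upward because it drops only event-free patients. Under these assumptions the crude 8.0% and the sensitivity 11.3% bracket the true 10%.

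**The case against.** The best reply is that note 4 never says monitoring stops. It speaks of procedures, and its example is the investigator's assessment. Monitoring is a separate, continuous row in the flow chart, and three other places require 72 (±6) hours. The endpoint's own parenthesis equates the final examination with the end of the follow-up period. SAP Section 11.1 sets only a lower time limit on the events it counts. SAE reporting has no stated end (Protocol Section 7.3.3), and ADRs after completion and deaths within four weeks are also reported (Section 7.3.7). On that reading little or nothing is lost.

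This stands as far as it goes: a reader might infer that the SAP discards events after an early examination, and no rule says so. But no text says such events enter the endpoint either, and post-study ADRs follow the post-marketing route. Non-serious TEs, TEEs and hyperfibrinolytic events not judged to be ADRs have no stated route once the clinical phase is complete.

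Three further replies are fair. The SAP does give completers, withdrawals by reason and individual time-scaled profiles, and its missing-data sentence does not forbid a summary of follow-up. If children discharged early are at lower risk, the bias is smaller than modelled; withdrawals also shorten observation and may act the other way. Finally, the SAP was written from protocol version 10 of 29-Nov-2017, whereas the protocol at hand is dated 19-Nov-2016, so note 4 may since have changed.

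**Conclusion.** The passages conflict on when observation ends, and they must be reconciled. If an early examination closes observation, the planned percentages can understate a primary safety endpoint, and no planned table would show how far.

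A reader might go further and conclude that the rates are biased downward, by as much as a third. The documents do not support that. They do not establish that monitoring stops early, and they give no frequency or timing of early examinations. The 33% figure needs half the patients examined at 24 hours, very short treatment and a constant event rate. The simple share of follow-up lost, 0.5 × (72 − 24)/72 = 33%, covers only the follow-up part of a window that can also include up to 72 hours of treatment.

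What can be said is conditional. With 10% true incidence and early examinations at 24 to 66 hours, relative bias ranges from under 1% to about 33%. It is at most about 11% in the front-loaded scenarios and is usually below sampling error at 50 patients. No hypothesis test is affected. The change is still worth making because it is cheap and concerns a primary endpoint.

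**What to change.** 1. In Protocol Section 3.1, note 4 and Section 6.1, and in SAP Section 3.2.1, define the event window as the start of the first infusion to 72 (±6) hours after the end of the last infusion, whatever the date of the examination. Say which infusion counts as the last, since Protocol Section 4.2 allows Octaplas during follow-up. After early discharge, complete the window by a chart check or brief contact.
2. In SAP Section 11.1, derive observation time from the first infusion to the last safety contact. Report the number of patients, overall and by subgroup, observed for less than 66 hours (72 − 6) after the last infusion.
3. Add the sensitivity incidence in fully observed patients, also keeping any patient who had an event before observation ended. Present it beside the crude percentage as an upward-leaning companion, not as a correction.

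Rates per patient-day are optional. The cost is one derived variable, one table and a short contact for patients discharged early. If it is too late for the contact, items 2 and 3 still show how much observation was lost.
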